### 339 3.3.2 Standard Procedure of lidocaine-ketamine infusions at the Pain Unit of USB

340  
341 During a short medical history interview Patients are briefly asked about their current pain  
342 situation before each infusion. For safety reasons, additional questions are asked about weight  
343 changes, compliance with fasting (= no solid food for 6 hours, no drinks for 2 hours) and allergies.

344 Monitoring is then installed (10-minute blood pressure measurement, continuous SPO2 and 5-  
345 lead ECG are recorded) and venous access is established. Lidocaine and ketamine are infused  
346 over a period of 30 minutes. The dosage of lidocaine is 4mg/kg is maintained throughout the  
347 infusions, and the dosage of ketamine is increased within the first three infusions from 0.15mg/kg  
348 at the first, to 0.25mg/kg at the second and 0.5mg/kg at the third infusion. In case patients already  
349 experiencing sufficient analgesic effect and/or improvement in quality of life after the 1st or 2nd  
350 infusion or if side effects do not allow a further dose increase, no further step up of ketamine  
351 dosage is made. We define a sufficient effect as a significant pain reduction (more than 50%) for  
352 at least 2 weeks and/or better quality of life with improved functionality during at least 2 weeks.

353 After the infusion, patients are monitored for at least another half hour, are discharged in company  
354 and are instructed to not run heavy machines and motor vehicles for at least 24 hours.

355

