	
The dosage regimens proposed in this recommendation are clearly exceeded by the standard regime at our pain unit (i.e. 4mg/kg lidocaine over 30 minutes). For note the new consensus statement addresses perioperative use of lidocaine in acute postoperative pain, and our treatment regime is based on previous studies investigating chronic pain. [9, 22] In addition, during a previous retrospective study at our Pain Unit, no serious adverse events were registered during 2995 infusions performed, rendering it a safe procedure. [23] Nevertheless, Foo, Macfarlane et al. defined a toxic lidocaine concentration in plasma as >5µg/ml. In order to assess whether this concentration is exceeded at the USB, the aim of this pilot project is to measure the lidocaine plasma level in a limited number of patients to generate explorative data on inter- and intrapersonal stability and safety of drug plasma levels. Beyond safety issues, we are interested in dosing and effects of our treatments. In the literature, there is evidence that higher doses of ketamine are associated with greater and longer pain relief, which is also consistent with the data from our retrospective study. [23, 24] As a standard regime of our infusion therapies, we increase the ketamine dose from 0.15mg/kg at the first infusion to 0.25mg/kg at the second infusion and 0.5mg/kg at the third infusion. Therefore, another aim of this study is to investigate whether higher plasma levels of ketamine can be correlated with a better analgesic effect.

Objective(s):
	
The primary objective of this study is to measure the concentration of lidocaine in the plasma of patients at the USB after an intravenous infusion with 4mg/kg lidocaine over 30 minutes.
 
We hypothesize that lidocaine concentrations in plasma of patients at the USB are inter- and intrapersonal stable and do not exceed 5µg/ml by the end of the applied infusions.
 
The secondary objectives of this study include the prospective side effects assessment of lidocaine and ketamine as well as the measurement of plasma levels of ketamine. Further, to correlate the plasma levels with the analgesic efficacy and change in possible depressive symptoms, due to the infusions.

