Statistical Considerations:	
Patients characteristics regarding to age, gender, pharmacological treatment, medical diagnosis will be analyzed exploratively/ descriptively.
 
Primary outcome:
 
The primary outcome (Lidocaine plasma level) of our study is explorative and not comparative, therefore, no H0 or H1 are formulated no power analysis is performed and only descriptive/ explorative statistics are reported.
 
We plan to include 10 patients with complete data sets, meaning, full data of three infusions with stable dose of lidocaine (4mg/kg/BW) and escalating dose of ketamine (0.15 – 0.5mg/kg/BW). This corresponds to thirty measures of lidocaine plasma concentrations at a dose of 4mg/kg/BW). Patients without full data sets will be replaced but data from patients with preliminary study termination will be reported in the final protocol.
 
Secondary outcomes:
 
 
1. Ketamine plasma levels are assessed according to lidocaine levels.
 
2. H0: dose escalation of ketamine has no effect on pain (outcome measure: SF-MPQ-2) and mood (outcome measure: BDI-II. H1: we hypothesize that ketamine dose has an effect on both outcome measures. For repeated measurements, an ANOVA will be separately calculated for outcome measures of pain and mood as dependent variable. This analysis will be performed separately for intermediate (one and two weeks) and
 

	
long term effects (four weeks). For comparative outcomes a level of significance of 0.05 will be used. In case of multiple testing a correction factor (in case of ANOVA: Bonferroni) for multiple testing is applied.
 
3. Side effects during treatment will be primary analyzed descriptively.
 
4. Multiple exploratory linear regressions will be calculated to evaluate the impact of dose and plasma levels of lidocaine and ketamine on pain and mood as well as occurrence of side-effects.
 
SPSS Version 25 will be used for data analyzation and graph pad PRISM Version 9 for data visualization. The investigators, [name] and [name], will perform all analysis steps. If needed, statistical guidance will be applied by statisticians of the Clinical Trial Unit (CTU) of the USB.
 
Handling of missing data:
 
Dropouts will be replaced. We do not plan data imputation.

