#### 400 **Secondary outcomes:**

401 1. Ketamine plasma levels are assessed according to lidocaine levels.

402

403 2. H0: dose escalation of ketamine has no effect on pain (outcome measure: SF-MPQ-2) and  
404 mood (outcome measure: BDI-II. H1: we hypothesize that ketamine dose has an effect on both  
405 outcome measures. For repeated measurements, an ANOVA will be separately calculated for  
406 outcome measures of pain and mood as dependent variable. This analysis will be performed  
407 separately for intermediate (one and two weeks) and long term effects (four weeks). For  
408 comparative outcomes a level of significance of 0.05 will be used. In case of multiple testing, a  
409 correction factor (in case of ANOVA: Bonferroni) for multiple testing is applied.

410

411 3. Side effects during treatment will be primary analyzed descriptively.

412

413 4. Multiple exploratory linear regressions will be calculated to evaluate the impact of dose and  
414 plasma levels of lidocaine and ketamine on pain and mood as well as occurrence of side-effects.

415

416 SPSS Version 25 will be used for data analyzation and graph pad PRISM Version 9 for data  
417 visualization. The investigators, [name] and [name], will perform all analysis  
418 steps. If needed, statistical guidance will be applied by statisticians of the Clinical Trial Unit (CTU)  
419 of the USB.

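### Ketamine dose at infusions 2 and 3 follows the patient's earlier response and tolerance, so the item 4 regressions on ketamine dose and raw plasma level cannot be read as effects of ketamine

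*Protocol*

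**What the plan says.** The default schedule is in Protocol section 3.3.2: "infusions, and the dosage of ketamine is increased within the first three infusions from 0.15mg/kg" "at the first, to 0.25mg/kg at the second and 0.5mg/kg at the third infusion". The same paragraph makes the next step conditional on how the patient did. After the first or second infusion, sufficient analgesia or improved quality of life stops the escalation, and so does poor tolerance: "infusion or if side effects do not allow a further dose increase, no further step up of ketamine". The response trigger is then specified: "We define a sufficient effect as a significant pain reduction (more than 50%) for" at least two weeks, and/or better quality of life with improved function over the same period. Section 1 gives the same rule.

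The Synopsis (Background and Rationale) and section 1 state an aim that uses these data: "another aim of this study is to investigate whether higher plasma levels of ketamine can be correlated with a better analgesic effect". The matching analysis is item 4 of the secondary outcomes (Synopsis, Statistical Considerations, and section 4.1): "Multiple exploratory linear regressions will be calculated to evaluate the impact of dose and plasma levels of lidocaine and ketamine on pain and mood", and on side effects as well. Item 4 does not mention the hold rule, earlier response or infusion number.

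The primary outcome paragraph of section 4.1 describes a complete data set as three infusions with stable lidocaine and escalating ketamine, and replaces patients without a full set. It does not say on which side a held patient falls.

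**The concern.** From infusion 2 on, the outcome helps to choose the exposure. Low doses collect patients who already responded or who tolerated ketamine badly. The top dose collects tolerant patients whose relief was insufficient. A regression of relief on dose or raw level then picks up who was held as well as what ketamine did.

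Section 3.1 recognises responder selection and answers it by enrolling only patients new to the infusions. That does not help here, because this selection arises after enrolment.

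The stake is a stated aim. Section 6.2 expects plasma levels, correlated with effects and side effects, to inform the unit's infusion regimens. An association with the wrong sign or size could mislead that use.

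**Working it through.** **Figures in the plan.** 10 patients x 3 infusions = 30 lidocaine measurements, as section 4.1 states. From section 3.3.2: ketamine steps of 0.15, 0.25 and 0.5 mg/kg, a full range of 0.5 - 0.15 = 0.35 mg/kg, and a hold at more than 50% relief or limiting side effects. The protocol gives no relief mean, SD or ketamine level, so everything below rests on assumptions.

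**Check 1: studies of the planned size.** 10 patients x 3 infusions, mean relief 30 points, between-patient SD 25, within-patient SD 15, level = dose/1.5 x lognormal variation (CV 30%), hold once relief exceeds 50%. About 34% of patients then end below 0.5 mg/kg.
- No true effect: the mean correlation of level with relief is -0.23 pooled and -0.47 at infusion 3 (negative in about 94% of studies).
- No true effect, mean relief varied from 20 to 40 points and SDs of 25/15 or 15/20: the infusion-3 correlation runs from -0.18 to -0.52.
- True gain of 10 points from 0.15 to 0.5 mg/kg: the pooled slope on dose gives about -11 points, with the wrong sign in about 80% of studies. With SDs of 15/20 it gives about +1.
- Same data, within-patient slope: about +14 for a true 10, and +3 for a true 0.
- Only patients who reach 0.5 mg/kg: +12.4 for a true 10.

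**Check 2: a separate large simulation.** 200,000 patients, mean relief 0.30 at 0.15 mg/kg, holds for both response and side effects. Slopes are fractional relief per mg/kg. The true slope is 0.30, which is 0.30 x 0.35 = 0.105, or 10.5 points over the range.

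| SD between / within patients | Pooled | Within patient | Reached 0.5 mg/kg only |
|---|---|---|---|
| 0.20 / 0.10 | -0.10 | +0.35 | +0.33 |
| 0.25 / 0.15 | -0.29 | +0.40 | +0.37 |
| 0.15 / 0.20 | +0.04 | +0.52 | +0.46 |
| 0 / 0.20 | +0.30 | +0.54 | not run |

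If every patient is escalated, the pooled slope recovers 0.30. The second row's -0.29 x 0.35 = -0.10, or -10 points, agrees with check 1. In 10-patient studies at those SDs the pooled slope has the wrong sign in about 73%, against 5% when all are escalated. With plasma level in place of dose, a true +0.30 becomes about -0.12. An improving trend of 0.05 per infusion moves the first row's -0.10 to +0.06.

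**Check 3: side effects.** The pooled slope of side-effect probability on dose falls from about 1.00 to 0.75 per mg/kg under the hold rule. With strong variation in sensitivity it goes from +0.37 to -0.57. In the first setting the within-patient slope rises to about 1.5, so the direction again depends on the model. A side-effect hold alone leaves the pain slope at 0.30 if tolerance is independent of response.

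**Check 4: variation that the dosing decision does not create.** Dividing the level by the mg/kg given removes the chosen dose. With no true effect, the correlation with relief averages 0.00 for infusion 1 and for the dose-normalised level at infusion 3. With a true gain of 10 points it averages only 0.05 and 0.12, with power of about 5-6% and 6-7% at alpha 0.05.

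Infusion 1 also meets the assay limit. The assumed mean level is 0.15/1.5 = 0.10 mg/L, equal to the ketamine LLOQ in section 3.3.3. With sigma = sqrt(ln(1 + 0.3^2)) = 0.294, the share below the LLOQ is Phi(0.294/2) = Phi(0.147) = 0.56.

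**The case against.** The strongest reply is that item 4 fixes very little. It calls the regressions exploratory and does not say whether they are pooled, within-patient or adjusted. Such detail is commonly left to a statistical analysis plan, and none is shown. That stands against any claim about one direction of bias. A reader might infer that the regressions are generally biased against a benefit. The documents do not support this: the same rule inflates a benefit in a within-patient analysis, and also if held patients are replaced, which is a literal reading of the complete-data-set definition. The reply does not rescue the interpretation. Item 4 sets out to evaluate the impact of dose and level, and none of these three simple choices recovers the truth once responses vary between patients.

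A reader might also infer that the selection cannot be reconstructed afterwards. That goes too far. Section 3.3.1 records weight and ketamine in mg, so a hold is visible. Pain at the start and at days 7 and 14, together with the side-effect lists, largely covers two of the triggers. Quality of life and function are not among the listed variables. Section 3.3 cites a separate eCRF forms document that is not at hand, so a reason field may already exist.

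It is also fair to say that the cleaner analysis is close to uninformative with 10 patients, and that infusion 1 alone may be largely unquantifiable. Both points stand and limit what the fix can deliver.

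**Conclusion.** The point holds as a cheap improvement. Ketamine dose at infusions 2 and 3 depends on earlier relief, quality of life and tolerance, so associations with raw ketamine dose or level are not effects of ketamine. Pooled or between-patient regressions understate an analgesic benefit and can reverse its sign: a true 10 points becomes about -11 to +1 in the settings of check 1. Within-patient analyses, or those limited to fully escalated patients, overstate it, at about +14 and +12. In pooled data, holds for side effects mask a dose relation of harm.

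The mechanism and these directions follow from the protocol's rule. The sizes rest on assumed relief means and SDs. With no between-patient variation in response, the pooled bias on pain disappears, and a trend over infusions would shift the results. The analyses are secondary and exploratory, and the primary lidocaine endpoint is not affected.

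**What to change.** Leave dosing practice as it is, and change the analysis text and one data field.

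1. In item 4, state that associations with raw ketamine dose or level across infusions are descriptive and are not effects of ketamine. Show held and escalated patients separately.
2. For the level-effect question, use the dose-normalised level (mg/L per mg/kg given) within each infusion. State that it assumes levels proportional to dose, that infusion-1 levels may lie near the 0.1 mg/L LLOQ, and that precision with 10 patients is very low.
3. At infusions 2 and 3, record whether ketamine was stepped up and why (sufficient relief, quality of life, side effects), unless the eCRF already does.
4. Reconcile the complete-data-set definition in section 4.1 with the hold rule in section 3.3.2: state that held patients count as complete and are not replaced.

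The cost is some wording and one extra eCRF field. The downside is a narrower and less precise level-effect analysis.

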### 356 3.3.3 Laboratory Analysis

357 Plasma concentrations of lidocaine and ketamine are determined at the Institute of clinical  
358 chemistry at University Hospital Zurich under ISO/IEC 17025:2017 accreditation.

359 The Plasma lidocaine and ketamine concentrations are measured using liquid chromatography  
360 coupled to high-resolution accurate mass-spectrometry (LC-MS).

361 For lidocaine measurement, 100uL of plasma samples are precipitated with 100uL acetonitrile  
362 (containing internal standard) and centrifuged. Supernatant is diluted with 5mM ammonium format  
363 buffer pH 3 for analysis.

364 For ketamine measurement, 1 mL of plasma samples are diluted with 0.5mL H2O and 0.5 mL  
365 ethanol (containing internal standard) extracted using e 150 µl 1 M NaOH in H2O and 5 ml n-  
366 Hexan/Dichlormethan (4+1, v+v). Supernatant was separated and dried down under steam of N2.  
367 For measurement, samples are reconstituted with acetonitrile and 10 mM ammonium acetate  
368 buffer.

369 Samples were analyzed on a Thermo Scientific™ Orbitrap Exploris™ 240 Mass Spectrometer  
370 coupled to reversed phase liquid chromatography with an LLOQ of 0.1 µmol/L for lidocaine and  
371 0.1 mg/L for ketamine. The methods were fully validated according to EMA guideline.

372 Both methods were fully validated according to EMA guideline.

373

### 374 3.4 Withdrawal and discontinuation

375 Patients may withdraw from the study at any time and for any reason (stating reason is not

376 required). No further data will be collected after withdrawal. Unless otherwise requested, the data  
377 collected up to that point will still be evaluated in encrypted form and anonymized after the  
378 evaluation.

379 The following reasons result in withdrawal:

- 380 • SAE
- 381 • AE challenging the health of the subject if continuing the study

382

383 Drop-outs will be replaced by new patients and will be reported in the final publication.

384

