#### 203 **2.1.2 Secondary objectives**

204 The secondary objectives of this study include the prospective side effects assessment of  
205 lidocaine and ketamine as well as the measurement of plasma levels of ketamine. Further, to  
206 correlate the plasma levels with the analgesic efficacy and change in possible depressive  
207 symptoms, due to the infusions.

[figure not shown]

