### 263 **3.3 Study procedures**

264 Recruitment and consent to participate in the study will take place in the consultation prior to the  
265 first infusion. (c.f. 3.2) During the infusion, the patients' vital signs will be monitored as usual (10-  
266 minute blood pressure measurement, continuous SPO2 and 5-lead ECG are recorded, c.f. 3.3.2).

267 As a part of this study, at the end of the first, second and third infusion, side effects will be  
268 screened using customized questionnaires (c.f. eCRF forms document). In addition, blood will be  
269 collected during each of the first three infusion appointments. The blood collection itself will take  
270 place within 3 minutes after termination of the infusion, as we assume the highest plasma levels  
271 at that point in time. [25, 26] For blood collection we will use a Butterfly cannula (BBraun Venofix®  
272 Safety 23G, PZN 08839883, B. Braun Melsungen AG) which will be inserted on the "non-infusion  
273 arm" and two green 7.5ml Lithium-Heparin monovettes (S-Monovette® Lithium-Heparin liquid,  
274 preparation: lithium heparin, liquid, 7.5 ml, membrane screw cap, closure green, color code ISO,  
275 (LxØ) without closure: 92 x 15 mm, with paper label, label/printing: green Sarstedt AG & Co. KG,  
276 Nümbrecht).

277 Patients will complete the Short form - McGill Pain Questionnaire (with additional recording of  
278 pain on the numeric rating scale (NRS) from 0 (no pain at all) to 10 (worst pain imaginable)) and  
279 Beck Depression Questionnaire directly prior to the first three infusions. The SF – MPQ is a  
280 validated instrument for measures of clinical pain that capture its sensory, affective and other

281 qualitative components. [27] The BDI-II provides a validated psychological test procedure that  
282 assesses the severity of depressive symptoms in adolescents 13 years of age and older and  
283 adults. [28]

284 In addition, these questionnaires will also be completed at the time points 7 days after, and 14  
285 days after the first, second and third Infusion. The participants will receive a link by e-mail so that  
286 they can fill in the questionnaires online. According to the license agreement, the BDI-II will be  
287 filled out in paper form and the results will be subsequently transferred to REDCap. If desired by  
288 the participant, these questionnaires can also be completed during a telephone survey conducted  

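### Section 3.4 makes an SAE or a health-challenging AE a withdrawal and stops all data collection at withdrawal, so a safety pilot ends observation of the patients with serious effects

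*Protocol*

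**What the plan says.** Section 3.4 opens with the patient's right to leave at any time and continues: "No further data will be collected after withdrawal". Data gathered before that point remain in use; that sentence begins "Unless otherwise requested, the data" and so allows the patient to refuse. A separate paragraph, introduced by "The following reasons result in withdrawal", has two entries: SAE, and "AE challenging the health of the subject if continuing the study". The section ends: "Drop-outs will be replaced by new patients and will be reported in the final publication".

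The synopsis (Statistical Considerations), repeated in section 4.1, adds: "Patients without full data sets will be replaced but data from patients with preliminary study termination will be reported in the final protocol". The target is 10 patients with full data from three infusions, and section 4.2 plans no imputation.

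On aims, section 2.1.2 states: "The secondary objectives of this study include the prospective side effects assessment of" lidocaine and ketamine. Section 2.1 hypothesises that lidocaine levels stay at or below 5 µg/ml at the end of infusion. Section 3.1 restricts entry to new recipients so as not to select responders or patients with fewer side effects.

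On timing, section 3.3 places the blood draw "place within 3 minutes after termination of the infusion, as we assume the highest plasma levels" at that point. Section 3.3.1 puts both side-effect checklists and the second ECG at the end of the infusion.

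**The concern.** Section 3.4 uses one word, withdrawal, for a patient's decision to leave and for the consequence of an SAE or serious AE. It attaches an unconditional end of data collection to that word. The infusions are standard care and the study is observational, so leaving the study means the end of observation. Stopping treatment, withdrawing consent and ending follow-up are not distinguished.

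The patients affected are those most informative for the safety aims. An uncollected plasma level, checklist or follow-up cannot be restored at analysis. The regressions of side effects on plasma levels in section 4.1 could lack the pairs at the serious end. Section 3.4 thereby lets back in, after enrolment, some of the selection that section 3.1 tries to keep out at entry.

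**Working it through.** **The plan's own figures.** 10 patients × 3 infusions = 30 lidocaine measurements, as stated. 10 × 1.5 = 15 patients at most, as stated. There is no power calculation to reproduce, and section 3.4 changes neither figure.

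**Is there an exception elsewhere?** Sections 5.2 and 5.3 cover protective measures, interruption of the project and notification. Neither provides for following the affected patient. The footnote defining a serious event limits it to events possibly attributable to sampling or data collection, so an event caused only by the infused drugs falls outside it. No exception was found.

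**What is kept.** Section 3.3 has continuous oxygen saturation and ECG and 10-minute blood pressure during the infusion. Section 7.2 lists AEs and SAEs among the source data. Section 3.4 keeps data up to withdrawal and reports drop-outs. A convulsion or arrhythmia during an infusion would therefore be on record and in the report.

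**What can be lost, counted from Appendix 1.** Samples fall on days 0, 28 and 56. Questionnaires fall on days 0, 7, 14, 28, 35, 42, 56, 63, 70 and 84, which is 10 sets. The set on an infusion day is completed before that infusion, so only later days count as lost.

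| Event at | Questionnaire sets still due | Samples not taken, withdrawal after the draw | Samples not taken, withdrawal before the draw |
|---|---|---|---|
| Infusion 1 (day 0) | 9 of 10 | 2 of 3 | 3 of 3 |
| Infusion 2 (day 28) | 6 of 10 | 1 of 3 | 2 of 3 |
| Infusion 3 (day 56) | 3 of 10 | 0 of 3 | 1 of 3 |

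**How much of this is due to the rule?**

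- *Infusions stop after the event.* Samples and checklists for infusions never given cannot exist under any wording. The part due to section 3.4 is the event infusion's own sample, checklist and ECG: 3 − 2 = 1 of 3 samples for an event at infusion 1, and likewise 2 − 1 = 1 and 1 − 0 = 1 in the other rows. It is 0 of 3 if withdrawal takes effect after the draw. Of the questionnaires, the sets on days 7 and 14 after the event infusion belong directly to it (and day 28 after infusion 3). Sets tied to infusions 2 and 3 could still be sent, but they no longer follow an infusion.
- *Infusions would have continued*, for example after an unrelated SAE between visits. Here the later samples, checklists and questionnaires are also lost because of the rule, up to the totals in the table.

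**How often?** The background reports no SAE in 2995 infusions. The one-sided 95% upper bound per infusion is 1 − 0.05^(1/2995) ≈ 0.10%. Over at most 15 × 3 = 45 infusions, the chance of any SAE is at most about 1 − 0.05^(45/2995) ≈ 4.4%, assuming independent infusions and comparable recording. This bound is retrospective. It does not cover the AE trigger, for which the protocol gives no rate, and it may not cover unrelated SAEs between visits.

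**The case against.** The no-further-data sentence directly follows the sentence on voluntary withdrawal and precedes consent language. The SAE/AE list is a separate paragraph. The authors may have meant the sentence for voluntary withdrawal only, and section 3.4 does not say when an SAE-driven withdrawal takes effect. The blood draw is timed from termination of the infusion, so a sample after an early stop already fits section 3.3. This stands as a plausible reading. But the text makes no exception, and on the milder reading data collection after an SAE is simply undefined, so the section needs rewording either way.

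Three stronger readings are tempting and are not supported:

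- A reader might infer that an affected patient leaves no side-effect record. Monitoring, AE/SAE source records, data up to withdrawal and the reporting of drop-outs contradict this.
- A reader might charge all 3 samples and all 3 checklists to the rule after an event at infusion 1. If infusions stop, two of each could never have been collected.
- A reader might argue that replacement turns 1 of 11 patients above 5 µg/ml (9%) into 0 of 10. That assumes an unmeasured level was above the threshold and ignores that drop-outs are reported. The one-sided 95% upper bound of 1 − 0.05^(1/10) ≈ 26% for 0 of 10 holds with or without section 3.4.

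It is also fair that not every patient with toxicity is lost. Those with milder effects stay in, and the AE trigger covers only events that endanger the patient if the study continues. In an emergency the sample may be impossible to take under any rule.

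**Conclusion.** The point holds in a limited form. As written, section 3.4 ends observation for patients with an SAE or a health-challenging AE, and no other section restores it. This conflicts with the study's safety aims and with the intent of section 3.1.

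The loss attributable to the rule is at most 1 of 3 samples, with that infusion's checklist and ECG, if infusions stop and withdrawal takes effect before sampling. To this are added the day 7 and 14 questionnaires after the event infusion, and up to 9 of 10 sets after an event at infusion 1. Later samples count only where infusions would have continued.

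The direction is towards a safer-looking result. The size cannot be determined from the protocol, and SAEs are probably rare. For a descriptive pilot that keeps and reports data up to withdrawal, this is a correction worth making, not a defect that invalidates the study. The conclusion assumes that the two paragraphs of section 3.4 use withdrawal in the same sense.

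**What to change.** In section 3.4, and correspondingly in the consent form:

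1. Apply the no-further-data sentence to withdrawal of consent only.
2. State that an SAE or AE does not by itself end data collection. Unless consent is withdrawn, and without delaying care, take the already planned sample when the infusion ends, recording elapsed infusion time and mg given. Complete the checklist and ECG, and continue the remaining questionnaires.
3. Report samples from shortened infusions separately from those after a full infusion.

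Whether and by whom infusions are stopped stays with the existing clinical rules; this change concerns data collection only.

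The cost is an amendment to the protocol and consent form, and a few samples that do not match the standard infusion. No new procedure is needed, because every assessment named is already scheduled. Samples from infusions that are never given remain missing.
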